9.5. Pharmacogenetics

Pharmacogenetic analyses will be performed on samples of patients who signed the dedicated informed consent. The candidate genes that will be analyzed may be related or hypothesized to be related to pharmacokinetics, safety features, drug mechanism of action, or related to study diseases. The final list of genes to be evaluated will be determined at the time of analysis to be able to account for the most current research. The planned pharmacogenetic analysis and results of other potential genetic factors will be detailed in a separate document that will encompass the latest scientific advances related to this evaluation.

For information regarding pharmacogenetic assessments, see [Appendix F](#).

10. STATISTICS

This section describes the statistical analysis methods for this study. Further details on analysis methods will be described in the Statistical Analysis Plan. Any changes or additions from the planned analysis methods described in the protocol will be disclosed in the Statistical Analysis Plan and in the clinical study report (CSR).

10.1. Sample Size and Power Considerations

A total study sample size of 240 patients is planned, with 120 patients (40 patients per dose arm) each for the 2 indications of UC and CD.

The sample size does not include patients that were randomized to the 1800 mg treatment group prior to Amendment 03 with Revision 01.

Assumptions:

The clinical remission and endoscopic response rates assumed in the sample size and related operating characteristics computations are as follows:

- Clinical remission rates in UC indication: 8% for placebo; 30% for TEV-48574 low- and high-dose groups, respectively
- Endoscopic response rates in CD indication: 12% for placebo; 34% for TEV-48574 low- and high-dose groups, respectively

Simulation-based operating characteristics for the analysis of the primary efficacy variable using a Bayesian Beta Binomial model are presented in [Table 8](#). This model uses a posterior probability cutoff of <0.30 for the assessment of futility at the interim analysis and a posterior probability cutoff of ≥ 0.90 to declare success at the final analysis.

For UC, the family-wise false-positive rate (ie, probability of making at least 1 false-positive conclusion under the null assumption for both doses) is 13%, and the probability of declaring success for at least 1 dose group is 98%, under the assumptions above.

For CD, the family-wise false-positive rate is 16%, and the probability of declaring success for at least 1 dose is 95%, under the assumptions above.

Table 8: Operating Characteristics of Interim and Final Analysis

	UC						CD					
	% F futile at interim analysis			% Success at end of trial			% F futile at interim analysis			% Success at end of trial		
	TEV-48574 doses											
	450 mg Q2W	900 mg Q2W	Both Doses	450 mg Q2W	900 mg Q2W	At least 1 dose	450 mg Q2W	900 mg Q2W	Both Doses	450 mg Q2W	900 mg Q2W	At least 1 dose
Null	25%	24%	11%	8%	8%	13%	24%	24%	12%	9%	10%	16%

	UC						CD					
	% F futile at interim analysis			% S successful at end of trial			% F futile at interim analysis			% S successful at end of trial		
	TEV-48574 doses											
	450 mg Q2W	900 mg Q2W	Both Doses	450 mg Q2W	900 mg Q2W	At least 1 dose	450 mg Q2W	900 mg Q2W	Both Doses	450 mg Q2W	900 mg Q2W	At least 1 dose
Intermediate efficacy both doses	4%	4%	1%	61%	61%	77%	4%	4%	1%	59%	59%	76%
Efficacy both doses	1%	1%	<1%	91%	91%	98%	1%	1%	<1%	87%	87%	95%

CD=Crohn's disease; Q2W=every 2 weeks; UC=ulcerative colitis.

Note: Beta-Binomial model with non-informative prior; posterior probability futility cutoff: <0.30; final analysis posterior probability cutoff of ≥0.90.

Note: Operating characteristics based on 500,000 simulations.

Under a less optimistic scenario where the placebo response rates remain the same while the clinical remission rate in the UC indication is reduced to 20% for both doses, and the endoscopic response rate in the CD indication is reduced to 25% for both doses, the probability of declaring success in at least 1 dose is 77% for UC and 76% for CD.

Details regarding the statistical decision criteria and Bayesian model, as well as operating characteristics in case only 1 active dose is effective are provided in [Appendix L](#).

For comparison, a frequentist logistic regression analysis with 40 patients per dose per indication would provide at least 90% power using a Mantel-Haenszel test with a 1-sided Type 1 error rate of 10% and the assumptions about response rate specified above. This power does not take into account the planned futility analysis.

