4. STUDY DESIGN

4.1. General Study Design and Study Schematic Diagram

This is a Phase 2b, randomized, double-blind, dose-ranging study to determine the pharmacokinetics, efficacy, safety, and tolerability of TEV-48574 in adult patients with moderate to severe UC or CD. The study will enroll adult patients (18 to 75 years of age, inclusive) of male and female sex (without restrictions on gender) with moderate to severe active UC or CD and who have demonstrated an inadequate response to, loss of response to, or intolerance to at least 1 of the following therapies: corticosteroids, immunosuppressants, or an advanced therapy for IBD including biologics (anti-TNF, anti-integrins, anti-IL-12/23 or anti-IL-23), JAK inhibitors, or sphingosine-1-phosphate (S1P) receptor modulators; and no more than 3 locally approved classes of biologics.

The study will consist of a screening period of up to 6 weeks (42 days), a 14-week treatment period, and a 4-week follow-up period.

Screening: After providing written informed consent, patients will be screened within 6 weeks (42 days) prior to randomization to confirm that they have met all the selection criteria for the study. At least 2 visits to the investigational site will be necessary to complete all screening procedures, including an endoscopy. The endoscopy should be performed after key eligibility criteria have been met and within approximately 10 calendar days of randomization (day 1) to allow for central endoscopy scoring.

Randomization: Patients satisfying the eligibility criteria at the end of the screening period will be randomized in a 1:1:1 ratio (stratified by diagnosis [UC or CD] and previous exposure to advanced therapy for IBD (yes/no) (biologics, JAK inhibitors, and S1P receptor modulators) to 1 of 3 treatment groups for the double-blind treatment period ([Table 2](#)).

All study treatments will be administered in a double-blind fashion as 1 sc infusion Q2W.

Table 2: Randomization Scheme

Randomization ratio	Planned approximate number randomized	Treatment (Q2W)
1	40 UC + 40 CD	TEV-48574 2250 mg (single loading dose)/900 mg (6 induction doses)
1	40 UC + 40 CD	TEV-48574 2250 mg (single loading dose)/450 mg (6 induction doses)
1	40 UC + 40 CD	Placebo

CD=Crohn's disease; Q2W=every 2 weeks; UC=ulcerative colitis.

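### The frequentist power of at least 90% in Protocol Section 10.1 is not reached in Crohn's disease, where the protocol's own inputs give about 86–87% per dose

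*Protocol*

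**What the plan says.** Protocol Section 10.1 plans "120 patients (40 patients per dose arm) each for the 2 indications of UC and CD". The assumed rates are:

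- UC: "Clinical remission rates in UC indication: 8% for placebo; 30% for TEV-48574 low- and high-dose groups, respectively"
- CD: "Endoscopic response rates in CD indication: 12% for placebo; 34% for TEV-48574 low- and high-dose groups, respectively"

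After the Bayesian operating characteristics, the section adds a frequentist benchmark. A logistic regression analysis "with 40 patients per dose per indication", it states, "would provide at least 90% power using a Mantel-Haenszel test with a 1-sided Type 1 error rate of 10" per cent, at the response rates listed above it. The section adds that this figure ignores the planned futility look.

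Section 10.5.4.3 defines the Cochran-Mantel-Haenszel (CMH) comparison as pairwise, each active dose against placebo, run separately for UC and CD. Section 4.1 gives the allocation: patients "will be randomized in a 1:1:1 ratio".

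**The concern.** The sentence puts one floor under two different comparisons. Both indications assume a difference of 22 percentage points, but the CD rates lie closer to 50%, so the binomial variance is larger and the power lower at the same sample size. A figure that just holds in UC will not hold in CD.

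The study is dose-ranging and declares success dose by dose, and Section 10.5.4.3 plans dose-versus-placebo tests at a one-sided nominal level of 0.1. A reader who takes the sentence at face value would put the risk of missing an effective CD dose in those tests at 10% or less.

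**Working it through.** **Inputs, all from the protocol.** n = 40 per arm per indication, one-sided alpha 0.10 (z = 1.2816) and no futility look (Section 10.1). Rates are UC 0.08 v 0.30 and CD 0.12 v 0.34 (Section 10.1). Allocation is 1:1:1 (Section 4.1). The comparison is pairwise within indication (Section 10.5.4.3).

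**Normal approximation with pooled variance under the null.** With p̄ the mean of p0 and p1:

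- SE0 = √(2·p̄·(1 − p̄)/n)
- SE1 = √((p0(1 − p0) + p1(1 − p1))/n)
- power = Φ(((p1 − p0) − 1.2816·SE0)/SE1)

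*UC, where the stated figure reproduces:*

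- p̄ = 0.19
- SE0 = √(2 × 0.19 × 0.81/40) = 0.0877
- SE1 = √((0.0736 + 0.2100)/40) = 0.0842
- (0.22 − 1.2816 × 0.0877)/0.0842 = 1.278, so power is 89.9%

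*CD, where it does not:*

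- p̄ = 0.23
- SE0 = √(2 × 0.23 × 0.77/40) = 0.0941
- SE1 = √((0.1056 + 0.2244)/40) = 0.0908
- (0.22 − 1.2816 × 0.0941)/0.0908 = 1.095, so power is 86.3%

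**Exact enumeration.** Sum the product of the two binomial probabilities over every outcome pair for which the uncorrected Mantel-Haenszel z is at least 1.2816. This gives 91.1% in UC and 87.2% in CD.

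**Does the choice of formula matter?** One-sided 0.10, 40 v 40:

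| Method | UC | CD |
|---|---|---|
| Pooled normal | 89.9% | 86.3% |
| Unpooled normal | 90.8% | 87.3% |
| Exact, uncorrected MH | 91.1% | 87.2% |
| Arcsine | 91.0% | 86.9% |
| Log odds ratio, Wald | 85.8% | 83.4% |
| Log odds ratio, score type | 93.5% | 88.9% |
| Mid-p | 90.7% | 86.0% |
| CMH, two homogeneous strata (simulated) | 91.0–91.1% | 87.1–87.3% |

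The highest CD value is 88.9%. With a continuity correction, which the protocol does not mention, CD falls to 81.2% and UC to 85.8%.

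**Sample size for 90% in CD.** The pooled formula gives 47 per arm and the unpooled formula 45. Exact MH power is 90.2% at 45, 89.8% at 46 and 90.4% at 47. So 45 to 47 per arm would be needed, against 40 planned.

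**Comparison with the protocol's own table.** Table 8 shows per-dose success of 91% in UC and 87% in CD for the rule of posterior probability at least 0.90. Enumerating that rule without the interim look gives 91.0% and 87.2%, almost the same as the one-sided 10% Mantel-Haenszel test. The frequentist benchmark therefore performs like the Bayesian rule in both indications.

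**The case against.** The strongest defence is that the sentence never says power for each dose. The phrase about patients per dose describes sample size, not the success event, and the surrounding text reports success for at least one dose (95% in CD and 98% in UC). On that reading the unadjusted one-sided 10% test gives 95.4% in CD and 97.6% in UC, and the claim is true. Pooling both doses against placebo also passes in CD, at 93.2–93.4%, and one test stratified across both indications gives 98.9%.

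These readings do not fit the text. The section names the at-least-one-dose criterion where it uses it, and does not do so here. Section 10.5.4.3 makes the CMH comparisons pairwise and separate by indication, which rules out pooling doses or indications. Covariate adjustment in the logistic model might raise power, but the figure is tied to a Mantel-Haenszel test and no covariate effects are given.

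What stands is the point about weight. The figure is a side comparison to a Bayesian design, and no success rule, stopping rule or sample size rests on it. Table 8, just above the sentence, already shows 87% per dose in CD, so an attentive reader can see the true level. That 87% also comes from a different decision rule and includes the futility look, so it supports the size of the gap but does not by itself prove the sentence wrong. The direct calculation does that.

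**Conclusion.** The claim is wrong as written for CD. At the protocol's own rates, sample size and alpha, power per dose in CD is 86.3% (pooled normal) to 87.2% (exact), which is 3.7 to 2.8 points below the stated floor. The corresponding miss rate is about 13–14%. In UC the claim holds: 89.9% by the approximation and 91.1% exactly.

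This rests on the pairwise dose-versus-placebo comparison within each indication, no continuity correction, no multiplicity adjustment, no futility look and 40 patients analysed per arm. The error is small, confined to one indication, and does not undermine the primary design.

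**What to change.** Replace the single figure in Section 10.1 with power by indication: about 90–91% per dose in UC and about 86–87% per dose in CD, for a one-sided 10% Mantel-Haenszel test of each dose against placebo, without continuity correction or multiplicity adjustment and ignoring the futility look. If success on at least one dose was intended, say so and give those figures instead (97.6% in UC and 95.4% in CD).

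The cost is one sentence and a slightly less favourable number for CD. Sample size, analysis and conduct stay as they are.

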10.2. Analysis Sets

10.2.1. Intent-to-Treat Analysis Set

The intent-to-treat (ITT) analysis set for each indication (UC or CD) will include all randomized patients.

In the ITT analysis set, patients will be categorized by treatment to which patients were randomized, regardless of which treatment they actually received.

Data collected from patients after treatment discontinuation will be included in the ITT analysis set.

10.2.2. Modified Intent-to-Treat Analysis Set

The modified intent-to-treat (mITT) analysis set for each indication (UC or CD) is a subset of the ITT analysis set including only patients who receive at least 1 dose of placebo, TEV-48574 450 mg (low dose), or TEV-48574 900 mg (high dose).

In the mITT analysis set, patients will be categorized by treatment to which patients were randomized, regardless of which treatment they actually receive.

10.2.3. Safety Analysis Set

The safety analysis set for each indication (UC or CD) will include all randomized patients who receive at least 1 dose of IMP.

In the safety analysis set, patients will be categorized by treatment actually received, regardless of the treatment to which they were randomized, unless otherwise specified.

10.2.4. Pharmacokinetic Analysis Set

All patients in the safety analysis set who have at least 1 measurable concentration of TEV-48574 will be included in the pharmacokinetic analysis set.

10.2.5. Pharmacogenetic and Biomarker Analysis Set

All patients in the safety analysis set who provided consent for pharmacogenetic or biomarker sampling will be included in the analysis of pharmacogenetic or biomarker data.

10.2.6. Immunogenicity Analysis Set

The immunogenicity analysis set will include all patients in the safety set who receive TEV-48574 and who have at least 1 reportable immunogenicity result.

10.3. Data Handling Conventions

For all variables, only the observed data from the patients will be used in the statistical analyses; ie, there is no plan to estimate missing data, unless otherwise specified. Detailed data imputation rules will be described in the Statistical Analysis Plan.

10.3.1. Handling Withdrawals and Missing Data

The mITT analysis set will be used for efficacy analyses. UC patients who did not complete evaluation for clinical remission at week 14 will be reported as non-remitters. CD patients who did not complete evaluation for endoscopic response at week 14 will be reported as non-responders.

10.4. Study Population

The ITT analysis set (Section 10.2.1) will be used for all study population summaries. Summaries will be presented by treatment group, pooled TEV-48574, and all patients, separately by indication (UC or CD) and pooled (UC and CD).

10.4.1. Patient Disposition

Data from patients screened; patients screened but not randomized and reason for not randomized; patients who are randomized/enrolled; patients randomized/enrolled but not treated and reason; patients in the ITT, safety, and other analysis sets; patients who complete the study; patients who withdraw from the study; and patients who discontinue IMP will be summarized using descriptive statistics. Data from patients who withdraw from the study or discontinue IMP will also be summarized by reason for withdrawal using descriptive statistics.

10.4.2. Demographic and Baseline Characteristics

Patient demographic and baseline characteristics, including detailed IBD history, general medical history, prior medications and therapies, and ECG findings, will be examined to assess the comparability of the treatment groups by treatment, underlying disease, and all patients using descriptive statistics. For continuous variables, descriptive statistics (number [n], mean, standard deviation, median, minimum, and maximum) will be provided. For categorical variables, patient counts and percentages will be provided. Categories for missing data will be presented if necessary.

10.5. Efficacy Analysis

10.5.1. Primary Estimand

Refer to Section [3.2](#) for the primary estimand for UC patients and CD patients.

10.5.2. Primary Endpoints and Secondary Endpoints

Refer to Section [3.1](#) for primary and secondary endpoints.

10.5.3. Exploratory Endpoints

Refer to Section [3.3](#) for exploratory endpoints.

10.5.4. Planned Method of Analysis

The mITT analysis set (Section [10.2.2](#)) will be used as the primary analysis set for all efficacy analyses. Summaries will be presented by treatment group, underlying disease, and for all patients.

Note that patients that were randomized to the 1800 mg treatment group are excluded from the mITT analysis set. Efficacy endpoints for these patients will be analyzed using descriptive statistics, in separate summary tables.

10.5.4.1. Primary Efficacy Analysis

A Beta-binomial model with a non-informative Beta(1,1) prior will be used to analyze the primary response endpoint, clinical remission (for UC) or endoscopic response (for CD), hereafter denoted as “response”. The model will be fit separately for each dose within each indication.

Inference will be based on posterior distribution of the response rates. A TEV-48574 dose will be declared successful at the final analysis if the posterior probability that the response rate in the TEV-48574 dose is higher than the response rate in the placebo arm is ≥ 0.90 . Put another way, the success criterion for each dose within indication can be written as:

Posterior Probability (TEV-48574 response rate – placebo response rate > 0) ≥ 0.90

The following quantities will be presented:

- Posterior means of the response rates for TEV-48574 high dose (900 mg Q2W), TEV-48574 low dose (450 mg Q2W) and placebo

- 95% credible intervals for difference in response rates (TEV-48574 doses – placebo)
- For each TEV-48574 dose, Posterior Probability (TEV-48574 dose – placebo response rate >0)

For further details, see [Appendix L](#).

10.5.4.2. Sensitivity Analysis

Tipping point analysis will be performed to test the robustness of the primary analysis to the imputation of patients that discontinue the study or have missing week 14 modified Mayo score (UC patients) or SES-CD (CD patients) data as non-responders.

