3.2. Primary Estimand

The primary estimand in this study is defined by the following attributes:

- **Treatment:** In both UC and CD indications, patients will be randomly assigned to receive any one of the study treatment regimens shown below, in a 1:1:1 ratio:
 - TEV-48574 2250 mg (single loading dose)/900 mg (6 induction doses)
 - TEV-48574 2250 mg (single loading dose)/450 mg (6 induction doses)
 - Matching placebo
- **Target population:** The target population comprises patients with a diagnosis of moderate to severe UC or moderate to severe CD.
- **Variable:** Response for the primary efficacy analysis is defined as clinical remission status at week 14 for UC patients or endoscopic response status at week 14 for CD patients.
- **Handling of intercurrent events:** Intercurrent events addressed here are (a) use of rescue medication; (b) important protocol deviations; (c) UC or CD related surgery; and (d) treatment discontinuation. These intercurrent events will be addressed as follows: (a) Patients who used rescue medications prior to their week 14 evaluation of response (clinical remission in the UC indication or endoscopic response in the CD indication) will be reported as non-responders, ie, the composite variable strategy; (b) Patients experiencing any important protocol deviations, namely, use or changes in other medications, will be analyzed as if the deviation had not occurred, ie, treatment policy strategy; (c) Patients undergoing UC or CD related surgery will be treated as non-responders, ie, the composite strategy; and (d) Patients discontinuing treatment, regardless of the reason, will be treated as non-responders, ie, the composite strategy.
- **Population-level summary:** The population-level summary of interest is the quantity *Posterior Probability* ($p_{d,i} - p_{0,i} > 0$) estimated from a Bayesian Beta-Binomial model for the response rate (clinical remission rate for UC, or endoscopic response rate for CD), $p_{d,i}$, where $i=UC, CD$ and $d=0,1,2$ represent placebo, TEV-48574 low dose (450 mg Q2W), and TEV-48574 high dose (900 mg Q2W), respectively.

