5.3. Withdrawal Criteria and Assessments/Procedures for the Patient

In accordance with the Declaration of Helsinki (in accordance with the applicable country's acceptance), patients may completely withdraw from the study (ie, with no further study participation or contact) at any time for any reason. Patients may also discontinue IMP and remain in the study for assessments after consultation with the investigator and/or sponsor. The investigator and/or sponsor may also discontinue a patient from IMP and/or withdraw a patient from the study in any of the following events:

- in the event of intercurrent illness, adverse events, pregnancy, or any other reason concerning the health or well-being of the patient that indicates to the investigator that continued participation is not in the best interest of the patient (see also Individual Stopping Rules can be found in Section 4.4.1);
- if the patient is noncompliant with the study procedures and assessments or protocol-defined study restrictions or prohibited concomitant medication

Patients who terminate the study should complete the safety and efficacy evaluations specified for early termination in the Study Procedures and Assessments schedule ([Table 1](#)) at the time they terminate study participation, and they will be encouraged to complete the follow-up period in the study.

Investigators are to discuss patients who may be considering discontinuing IMP or withdrawing completely from the study with the sponsor as soon as the site becomes aware of the situation.

Investigators should attempt to obtain information on patients in the case of withdrawal from the study or discontinuation from IMP. Results of any evaluations and observations, together with a narrative describing the reason(s) for withdrawal from the study or discontinuation from IMP, should be recorded in the source documents. The CRF should document the primary reason for withdrawal from the study or discontinuation from IMP.

See [Appendix E](#) for information regarding how the study will define and address lost to follow-up patients to help limit the amount and impact of missing data.

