6.6.3. Permitted Inflammatory Bowel Disease Medications and Rescue Medications

Permitted concomitant treatment for UC and CD must remain at a stable dose (no increase or decrease) during the study treatment period (except for decreases due to adverse events); if doses are increased, patients must be withdrawn from the study. The dose of any background medication for UC and CD should not be changed during the screening and double-blind treatment period. If a patient requires initiation of a new therapy for UC or CD, the patient should be withdrawn from the study, and appropriate treatment should be administered at the discretion of the investigator.

Patients will be allowed to use the following medications as detailed below:

- Concomitant use of oral 5-ASA or sulfasalazine. Dose must be stable for at least 4 weeks prior to endoscopy and through week 14. If oral 5-ASA treatment has been recently discontinued, it must have been stopped for at least 2 weeks prior to endoscopy.
- A stable dose of oral corticosteroids (prednisone equivalent of up to 20 mg/day; budesonide of up to 9 mg/day) for at least 2 weeks prior to endoscopy and through week 14. If oral corticosteroids have been recently discontinued, they must have been stopped at least 2 weeks prior to endoscopy. Decreases in steroid use due to adverse events are allowed.
- A stable dose of immunosuppressant drugs (methotrexate, 6-MP, or AZA consistent with regional standard of care) for 4 weeks prior to endoscopy and through week 14. Decreases due to adverse events are permitted.

Following the week 14 visit if not continuing on to the long-term extension study, patients will no longer need to abstain from the medications that were prohibited or required no change in dose during the screening and induction period. Biologic treatment(s) should not be initiated during the follow-up period without discussion with the sponsor.

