6.6.4. Prohibited Medications and Therapies

The following medications will be prohibited during this study:

- Any live (attenuated) vaccines from 14 days prior to the first screening visit and throughout the study.
- Topical (rectal) treatment of 5-ASA or intravenous, intramuscular (parenteral), or enema/suppository administration of corticosteroids within 2 weeks prior to endoscopy through week 14.
- Prednisone dose of >20 mg/day or equivalent oral systemic corticosteroid from 2 weeks prior to endoscopy through week 14.
- The patient is currently using any systemic immunosuppressant or immunomodulatory biologic or nonbiologic (other than those listed in inclusion criterion “h” and those that are used for IBD) within 30 days or 5 half-lives (whichever is longer) prior to the endoscopy.
- Biologics including anti-TNF, anti-integrins, anti-IL-12/23, or anti-IL-23 within 3 half-lives prior to randomization.
- Small molecules including JAK inhibitors, or S1P receptor modulators, within 5 half-lives or shorter washout duration if undetectable drug levels can be demonstrated prior to randomization.
- Oral budesonide of >9 mg/day or equivalent from 2 weeks prior to endoscopy through week 14.
- Patients requiring a surgical intervention for UC or CD will be discontinued from the study

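### The tipping-point analysis mixes patients whom the primary estimand already defines as non-responders with patients whose week 14 outcome is truly missing

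*Protocol*

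**What the plan says.** Section 3.2 of the protocol lists four intercurrent events and handles three of them by a composite strategy:

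- (a) Patients who use rescue medication before the week 14 evaluation "will be reported as non-responders, ie, the composite variable strategy".
- (c) "Patients undergoing UC or CD related surgery will be treated as non-responders, ie, the composite strategy".
- (d) "Patients discontinuing treatment, regardless of the reason, will be treated as non-responders, ie, the composite strategy".

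Event (b), important protocol deviations, follows treatment policy.

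Section 10.3.1 separately counts patients who did not complete the week 14 evaluation as non-remitters (UC) or non-responders (CD). That is the missing-data rule.

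Section 10.5.4.2 then plans a tipping-point analysis of the robustness of the primary result "to the imputation of patients that discontinue the study or have missing week 14 modified Mayo score" (UC) or SES-CD (CD) as non-responders. The section does not mention intercurrent events.

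Three other rules decide who enters that set. Section 6.6.3: "If a patient requires initiation of a new therapy for UC or CD, the patient should be withdrawn from the study". Section 6.6.4: "Patients requiring a surgical intervention for UC or CD will be discontinued from the study". Section 5.3: "Patients may also discontinue IMP and remain in the study for assessments after consultation with the investigator and/or sponsor".

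**The concern.** Under a composite strategy the intercurrent event is part of the outcome. A patient who stops treatment in week 6 is a non-responder by definition, and no later observation could change that. A sensitivity analysis should vary the assumption that cannot be verified while the estimand stays fixed. Here that assumption is the non-response assigned to patients who had no composite event and whose week 14 score is absent. Switching a treatment discontinuation to a response changes the variable in Section 3.2 and so answers a different question.

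The stake is how a positive result is read. A success could be reported as tipping after a handful of switches when few or none of the switched patients had a missing outcome.

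**Working it through.** **1. Who is in the set.** Section 4.1 puts the last dose on day 85 and the readout on day 99.

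| Patient | Outcome under Section 3.2 | In the tipping-point set? |
|---|---|---|
| Leaves the study before the day 85 dose | Known: non-responder, event (d) | Yes |
| Has UC or CD surgery and is discontinued (6.6.4) | Known: non-responder, event (c) | Yes |
| Withdrawn after starting a new UC or CD therapy as rescue before week 14 (6.6.3) | Known: non-responder, event (a) | Yes |
| Stops treatment, stays, has a week 14 score (5.3) | Known: non-responder, event (d) | No |
| Completes dosing, no composite event, no week 14 score | Missing | Yes |
| Leaves between day 85 and day 99, no rescue or surgery, no week 14 score | Missing | Yes |

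Only the last two rows have a missing outcome. The first and fourth rows share the same event and the same estimand outcome, yet only the first may be varied.

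**2. Inputs for the size.** Section 10.1 gives 40 per arm per indication, UC rates of 8% v 30% and CD rates of 12% v 34%, and an intermediate scenario of 20% (UC) and 25% (CD) on active. Section 10.5.4.1 gives the Beta(1,1) prior and success at a posterior probability of 0.90 or more. No dropout rate is stated.

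**3. Formula.** With x1 responders on active, x0 on placebo and n = 40 in each arm,

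P(p1 > p0) = ∫ f(p; 1 + x1, 1 + n − x1) · F(p; 1 + x0, 1 + n − x0) dp over 0 to 1,

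where f and F are the Beta density and distribution function.

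**4. Reproducing the plan's figures.** Exact enumeration of this rule, with the placebo arm shared between doses, gives the following probabilities of success, with and without the interim futility rule:

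- UC, planned effect: 97.5% to 97.6% for at least one dose, 91% per dose (Table 8: 98% and 91%).
- CD, planned effect: 95.4% and 87% (Table 8: 95% and 87%).
- Null, at least one dose: 13.5% UC and 16.0% CD (Table 8: 13% and 16%).

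The model is therefore read correctly.

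**5. Switching placebo non-responders, active arm held fixed.** Starting counts are the rates times 40, rounded: 0.30 × 40 = 12 and 0.08 × 40 = 3.2, so 12 v 3; 0.34 × 40 = 13.6 and 0.12 × 40 = 4.8, so 14 v 5; 0.20 × 40 = 8, so 8 v 3; 0.25 × 40 = 10, so 10 v 5.

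| Scenario | Start | After 1, 2, 3, ... switches | Falls below 0.90 at |
|---|---|---|---|
| UC planned, 12 v 3 | 0.995 | 0.986, 0.970, 0.943, 0.901, 0.844 | 5 (5/40 = 12.5% of the arm) |
| CD planned, 14 v 5 | 0.990 | 0.979, 0.960, 0.930, 0.888 | 4 (4/40 = 10%) |
| UC intermediate, 8 v 3 | 0.942 | 0.887 | 1 |
| CD intermediate, 10 v 5 | 0.919 | 0.862 | 1 |

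If every switched patient had a composite event, the restricted analysis has nobody to vary and the posterior stays at its starting value in each row.

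**6. Direction matters.** Switching only placebo is the least favourable choice. From 10 v 5, one placebo switch gives 10 v 6 = 0.862, below the cutoff. Switching one active patient as well gives 11 v 6 = 0.909, which still succeeds.

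**The case against.** The strongest reply is that the planned analysis covers a superset and loses little. The posterior depends only on responder counts, so the number of switches that tips the result is the same whichever non-responders are switched. A reader might infer that this number would never be reported; that is not so. What is not shown is how many patients are truly missing, and hence whether they could reach the number. Section 10.4.1 promises withdrawals and treatment discontinuations by reason, which helps but does not isolate patients with no composite event and no score.

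A reader might also infer that this is the only robustness check planned. Section 10.5.4.3 adds a covariate-adjusted logistic regression and a CMH test of the same variable. Neither probes missing data, so Section 10.5.4.2 is the only missing-data sensitivity analysis and no more than that.

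Third, the section does not name rescue or surgery. Such patients enter through the withdrawal rules, and some members of the set are proper targets. This stands: the set is mixed, in proportions that the protocol does not give.

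Finally, Sections 10 and 10.3 leave method detail and imputation rules to the SAP, which was not available. Grid and display may well be there. But Section 10.5.4.2 itself fixes who is varied, so the population is not an open detail.

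**Conclusion.** The point holds as one of alignment between estimand and analysis. The tipping-point set combines patients whose outcome Section 3.2 defines with patients whose outcome is missing, and the result will not separate them.

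It would be wrong to conclude that the success declaration is at risk. Success is fixed by the posterior rule in Section 10.5.4.1, no decision rule is attached to the tipping point, and the wider set can only make a positive result look more fragile. It cannot create a false success.

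The size is illustrative: 5 (UC) or 4 (CD) placebo switches out of 40 at the planned effects, and 1 in the intermediate scenario. These counts assume expected responder numbers, placebo-only switching and enough placebo patients in the set. How often this would matter depends on a dropout rate, and on a split between composite events and missing scores, that the protocol does not state.

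**What to change.** Amend Section 10.5.4.2, or state in the SAP as a disclosed change, that:

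- the tipping-point analysis varies only patients with a missing week 14 modified Mayo score or SES-CD and none of events (a), (c) or (d);
- patients with a composite event stay non-responders throughout;
- both arms are varied, and the number of truly missing patients per arm is reported beside the grid.

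Any wider version that also switches discontinuations should be labelled supplementary and given its own estimand. The existing supplementary estimand in Section 3.2.1 cannot serve, because it keeps the same intercurrent-event handling.

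The cost is a short change of text, with no new data. The downside is that the restricted analysis covers fewer patients and is a milder stress test. The labelled supplementary version can restore that.
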